4.5.1. Dose Delays

Participants who experience toxicity should have study drug held pending assessment, management, and resolution of the toxicity. If the toxicity is assessed as unrelated to study drug or does not meet DLT criteria, study drug may be restarted at the previous dose and schedule, after consultation with the medical monitor. The toxicity should have resolved prior to reinstitution of study drug per guidelines outlined in Section 7. Reinstitution of study drug shall be conducted as follows:

• Dose delays of up to 21 days are allowed for participants who experience toxicity. This may include 1 missed dose of IMGC936 on Schedule A and 2 missed doses on Schedule B. The procedures at the originally scheduled missed visit should be performed as soon as possible with study drug reinstituted as if no delay had occurred, picking up at the day where the interruption occurred per the schedule in Appendix 1 and Appendix 2. Participants who have a dose delay of > 21 days may restart study drug with discussion and approval of the sponsor.

4.5.1.1. COVID-19/SARS-CoV-2 Infection

The following guidelines apply to participants with confirmed (positive by regulatory authority approved test) or presumed (test pending/clinical suspicion) coronavirus disease 2019 (COVID-19)/severe acute respiratory syndrome coronavirus 2 (SARS-CoV-2) infection:

- For participants with active SARS-CoV-2 infection, study drug should be delayed for at least 14 days from the first positive COVID-19 test or start of symptoms whichever is later.
- Prior to restarting study drug, participants should be afebrile for 72 hours and SARS-CoV-2—related symptoms should have recovered to ≤ Grade 1 for a minimum of 72 hours. The sponsor should be informed when resuming study drug.

The sponsor must be informed of a participant with COVID-19/ SARS-CoV-2 infection.

4.6. Study Duration

It is expected that enrollment for the Dose Escalation Phase of the study will occur over approximately 24 months. Enrollment for study expansion will occur over approximately

18 months. The total time for conduct of the trial is expected to be approximately 48 months. These time estimates may vary from that observed in the actual conduct of the trial.

4.6.1. Participant Accrual

During dose escalation, the number of participants could be up to 45 depending on results during the study and the number of dose levels explored. If Schedule B is explored, up to 27 evaluable participants may be enrolled. This number does not consider replacement of non-evaluable participants or the possibility of expanding an individual escalation cohort up to 15 participants to allow for further evaluation of safety, PK, and antitumor activity at that dose level.

For study expansion, based on futility assessments at 13 participants per cohort for the 5 to 7 expansion cohorts, and at the sponsor's discretion, an additional 26 participants may be enrolled in each selected expansion cohort (for a total of up to 39 participants per cohort if fully expanded). The number of participants may vary depending on results of futility assessments. Up to 273 participants will be enrolled in the dose expansion cohort.

4.6.2. Definition of End of Study

The end of study will occur after the Safety Follow-up Visit for the last participant remaining on treatment or 1 year from the last accrued participant's first visit, or at the sponsor's discretion.

End of study for each participant is defined as follows: Participant is lost to follow-up (LTFU) (Section 9.15.3) or discontinues from the study due to any reason listed in Section 6.5. Each participant's end of study status will be recorded in the end of study electronic case report form (eCRF) page.

5. SELECTION AND WITHDRAWAL OF PARTICIPANTS

To be eligible for the study, participants must meet all the inclusion criteria. Participants will be excluded from the study if they meet any exclusion criteria. No exceptions to these criteria will be granted by the sponsor.

5.1. Inclusion Criteria

- 1. Ability to provide informed consent and documentation of informed consent prior to any study-related tests or procedures that are not part of standard of care for the participant's disease. Participants must be willing and able to comply with study procedures.
- 2. Participants with histologically proven, relapsed or refractory, unresectable locally advanced or metastatic non-squamous NSCLC, TNBC, CRC, gastroesophageal cancer, or pancreatic cancer for whom no therapy with demonstrated clinical benefit is available. Participants in expansion cohorts must have received all appropriate approved therapy and fit within the prior lines of therapy restrictions listed below.

Note: Neoadjuvant/adjuvant systemic treatment are included as 1 line in prior lines of therapy, except for TNBC where they are excluded.

Note: Maintenance therapies are considered part of the prior line of therapy and will not be counted as a separate line of therapy.

- a. Non-squamous NSCLC: Participants in dose expansion phase may have been treated with up to 3 prior lines of systemic chemotherapy, with no limit on prior targeted therapy containing lines, eg, for targetable mutations.
- b. TNBC: Participants in dose expansion phase may have been treated with up to 4 prior lines of systemic therapy for metastatic disease, excluding checkpoint inhibitors and neoadjuvant/adjuvant therapies.
- c. CRC: Participants in dose expansion phase may have been treated with up to 4 prior lines of systemic therapy.
- d. Gastroesophageal cancer: Participants in dose expansion phase may have been treated with up to 4 prior lines of systemic therapy.
- e. Pancreatic cancer: Participants in dose expansion phase must have been treated with 1 to 3 prior lines of systemic therapy, with no more than 2 chemotherapy-containing lines.
- 3. Either non-measurable or measurable disease per RECIST v1.1 and documented by computed tomography (CT) and/or magnetic resonance imaging (MRI) obtained within 28 days of Cycle 1 Day 1.
 - a. Dose Escalation Phase: Participants may have non-measurable or measurable disease per RECIST v1.1.
 - b. Dose Expansion Phase: Participants must have measurable disease per RECIST v1.1.
- 4. Age \geq 18 years old.
- 5. Tumor tissue must be submitted. If archival tissue (formalin-fixed paraffin-embedded [FFPE] block or slides) is not available, participants may undergo a low-risk, medically routine procedure, if appropriate.

- a. For all participants, tumor specimens for retrospective determination of ADAM9 expression via IHC staining will be collected and assayed at a central laboratory designated by the sponsor.
- 6. Eastern Cooperative Oncology Group (ECOG) performance status of 0 or 1.

Note: If ECOG performance status is an inappropriate performance measurement for participant enrollment (eg. chronically non-ambulatory), then Karnofsky performance status must be ≥ 70 .

7. Life expectancy > 12 weeks.

IMGC936

- 8. Acceptable laboratory parameters as follows:
 - Platelet count $> 75 \times 10^3 / \mu$ L without platelet transfusion within 28 days prior to initiation of study drug.
 - Absolute neutrophil count $\geq 1.5 \times 10^3 / \mu L$ in the absence of any growth factor support within 21 days prior to initiation of study drug.
 - ALT/AST $\leq 3.0 \times$ ULN; for participants with hepatic metastases, ALT and $AST \le 5 \times ULN$.
 - Total bilirubin $\leq 1.5 \times ULN$, except participants with Gilbert's syndrome, who may enroll if the conjugated bilirubin is within normal limits.
 - Estimated glomerular filtration rate (eGFR) > 30 mL/min/1.73 m² or an estimated creatinine clearance of > 30 mL/min.
 - Urinalysis protein and occult blood cells within normal limits or 1+.
 - Negative serum pregnancy test for females of childbearing potential (FOCBP).
- 9. FOCBP, defined as not surgically sterilized (hysterectomy, bilateral salpingectomy, and bilateral oophorectomy) and between menarche and 1-year post menopause, must have a negative serum pregnancy test performed within 72 hours prior to initiation of study drug administration. Female participants must abstain from egg donation during the study.
- 10. FOCBP and male participants with partners of FOCBP must agree to use highly effective methods of contraception, according to Section 8.1.3, from the time of consent through 28 weeks after discontinuation of study drug administration. Male participants must abstain from sperm donation during the study.
- 11. FOCBP is not pregnant or breastfeeding, or a male participant is not expecting to father children within the projected duration of the study, starting with screening visit through 28 weeks after the last dose of study drug.

5.2. **Exclusion Criteria**

Participants who meet any of the following criteria will be excluded from the study.

1. Participants with active central nervous system disease within the last 6 months.

- Active or chronic corneal disorders, history of corneal transplantation, or active ocular conditions requiring ongoing treatment/monitoring, such as uncontrolled glaucoma, wet age-related macular degeneration requiring intravitreal injections, active diabetic retinopathy with macular edema, macular degeneration, presence of papilledema, and/or monocular vision.
- 3. Participants who had prior therapies within the specified times below:
 - Systemic antineoplastic therapy within at least 5 half-lives or 4 weeks (whichever is shorter) prior to initiation of study drug.
 - Mediastinal or pelvic radiation therapy within 6 weeks prior to initiation of study drug administration. Palliative, limited field radiation for symptom control to soft tissues, or bone lesions within 2 weeks prior to initiation of study drug.
 - Note: Previously irradiated lesions are not considered measurable disease unless they have demonstrated progression per RECIST v1.1.
- 4. Participants must have stabilized or recovered (Grade 1 or baseline) from all prior therapy-related toxicities (except alopecia).
- 5. Clinically significant cardiovascular disease including but not limited to:
 - Myocardial infarction or unstable angina within 6 months prior to initiation of study drug.
 - Stroke or transient ischemic attack within 6 months prior to initiation of study drug.
 - Current clinically significant cardiac arrhythmias, eg, atrial fibrillation that are not well controlled with optimal medical intervention.
 - Current uncontrolled hypertension: systolic blood pressure > 160 mmHg, diastolic blood pressure > 100 mmHg.
 - Current congestive heart failure (New York Heart Association class III-IV).
 - Current pericarditis or clinically significant pericardial effusion.
 - Current myocarditis.
 - Left ventricular ejection fraction (LVEF) of < 50% by scan.
 - QTc interval > 480 msec.
- 6. Clinically significant pulmonary compromise, including pneumonia, pneumonitis, or a requirement for supplemental oxygen (excluding for sleep apnea) or history of ≥ Grade 3 drug-induced or radiation pneumonitis.
- 7. Participants with serious concurrent illness or clinically relevant active infection, including, but not limited to the following:
 - Active hepatitis B or C infection (whether or not on active antiviral therapy).
 - Human immunodeficiency virus infection.
 - Cytomegalovirus infection.

- Active COVID-19/SARS-CoV-2 infection. While SARS-CoV-2 testing is not mandatory for study entry, testing should follow local clinical practice guidelines/standards.
- Any other concurrent infectious disease requiring IV antibiotics within 2 weeks prior to initiation of study drug.

Note: Testing at screening is not required for the above infections unless clinically indicated.

- 8. History of prior bone marrow, stem cell, or solid organ transplantation.
- 9. Second primary invasive malignancy that has not been in remission for greater than 2 years, except nonmelanoma skin cancer; cervical carcinoma in situ on biopsy; or squamous intraepithelial lesion on Pap smear; localized prostate cancer (Gleason score < 6); or resected melanoma in situ or similar.
- 10. Major trauma or major surgery within 4 weeks prior to initiation of study drug.
- 11. Any serious underlying medical or psychiatric condition that would impair the ability of the participant to receive or tolerate the planned treatment at the study site.
- 12. Prior life-threatening hypersensitivity reactions to antibodies or any excipient contained in the drug formulation (Section 6.5).
- 13. Vaccination with replication-competent live virus vaccine within 4 weeks prior to initiation of study drug. Not all vaccine adverse effects have resolved to Grade 1. Inactivated annual influenza non-live vaccination is allowed (Section 8.1.1).

5.3. Withdrawal of Participant from the Study

Participants who withdraw before Cycle 1 Day 21 (Schedule A) or Cycle 1 Day 28 (Schedule B) for a reason unrelated to drug toxicity may be considered to have inadequate data to support dose escalation. These participants will be followed for safety assessments (see Section 12.2) and replacement participants may be enrolled in the same dose level.

5.4. Guidelines for Study Drug Discontinuation

Participants who tolerate study drug may continue to receive the study drug, as specified in the protocol, until any one of the following conditions are met:

- Progressive disease (PD) Objective progression per RECIST v1.1 or clinical progression as determined by investigator
 - Participants who experience PD by RECIST v1.1 should discontinue study drug.
 However, participants who have experienced clinical benefit may continue the treatment if agreed upon between the sponsor and the investigator
- AE requiring study drug discontinuation including, but not limited to, the following events:
 - Study drug-related ≥ Grade 3 cardiac event

- Study drug-related Grade 4 non hematologic event
- DLT during dose-escalation window (DLT period)
- Pregnancy
- Death
- Investigator decision
- LTFU
- Major protocol deviation requiring study drug discontinuation
- Participant declining further treatment
- Participant decision to withdraw consent for study
- The sponsor, investigator, or regulatory agency terminate the study

If the investigator decides that the participant should be withdrawn from the study or from dosing for any reason other than disease progression, the sponsor or its designee must be alerted in a timely manner by completing the appropriate eCRFs.

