4.2. Dose-Limiting Toxicity

For guiding dose-escalation decisions, DLTs will be defined based on TEAEs or abnormal laboratory values that meet DLT criteria that occur up to Day 21 of Cycle 1 for Schedule A and Day 28 of Cycle 1 for Schedule B. AE severity will be graded according to National Cancer Institute (NCI) Common Terminology Criteria for Adverse Events version 5.0 (CTCAE v5.0). DLTs will be defined separately for hematologic, non-hematologic, and hepatic events.

In addition to conventional Cycle 1 DLTs to guide escalation, cumulative toxicity and tolerability for all cohorts will be considered and may be utilized to inform dose escalation.

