4.2.1. Hematologic Dose-Limiting Toxicity

Hematologic DLT is defined as follows:

- Grade 4 neutropenia lasting > 7 days
- \geq Grade 3 febrile neutropenia Grade 4 thrombocytopenia, irrespective of duration
- Grade 3 thrombocytopenia associated with clinically significant bleeding
 - \geq Grade 3 hemolysis

The following events will be specifically **excluded** from the definition of hematologic DLT:

- ≥ Grade 3 lymphopenia
- Grade 3 anemia that is not associated with other clinically significant complications

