4.2.2. Non-hematologic Dose-Limiting Toxicity

Non-hematologic DLT is defined as any \geq Grade 3 non-hematologic event, including Grade 3 ocular symptoms and signs.

The following events will be specifically excluded from the definition of non-hematologic DLT:

- Grade 3 electrolyte abnormality that lasts < 72 hours, is not otherwise associated with clinical complications, and responds to medical intervention
- Grade 3 fever that lasts < 72 hours and is not associated with hemodynamic compromise
- Grade 3 nausea or vomiting that lasts < 72 hours and responds to medical intervention
- Grade 3 or greater amylase and/or lipase elevation that is not associated with clinical or radiographic evidence of pancreatitis requiring hospitalization
- Grade 3 gastrointestinal AEs of diarrhea, constipation, abdominal pain, cramping, dyspepsia, or dysphagia that resolves to ≤ Grade 1 or baseline within 72 hours with maximal supportive care
- Grade 3 fatigue that lasts < 72 hours

Note: The following Grade 2 non-hematologic AEs may also be considered as DLTs:

- Grade 2 AEs that are prolonged inordinately, based upon the medical judgment of the investigator, and/or lead to permanent discontinuation of study drugs due to participant intolerance
- Hepatic laboratory abnormalities meeting Hy's law criteria (described within Section 4.2.3)
- Eye pain or reduction in visual acuity that does not respond to topical ophthalmic therapy and does not improve to Grade 1 within 14 days of initiation of topical ophthalmic therapy, or that requires systemic treatment

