7.2.2. Management of Ocular Symptoms and Signs

Table 7: Management of Ocular Symptoms and Signs

Grade (CTCAE v5.0)	Management	Guidelines for Dose Modification ^a
Grade 1	Complete eye examination. Participants should have weekly symptomatic ocular assessments to monitor for worsening symptoms and signs and repeat eye examinations as needed.	Continue study drug dosing.
Grade 2	Complete eye examination. Participants should have weekly symptomatic ocular assessments and repeat eye examinations at least every 6 weeks until resolved to Grade 1 or less, stabilized, or returned to baseline, even after treatment discontinuation, if needed.	Hold study drug dosing until AE has resolved to ≤ Grade 1. Participants whose ocular symptoms and signs resolve to ≤ Grade 1 in ≤ 14 days may be allowed to resume study drug at the same dose level. Participants whose ocular symptoms and signs resolve to ≤ Grade 1 in > 14 and ≤ 28 days may resume study drug at 1 lower dose level with sponsor approval.
Grade 3	Complete eye examination. Participants should have weekly symptomatic ocular assessments and repeat eye examinations at least every 6 weeks until resolved to Grade 1 or less, stabilized, or returned to baseline, even after treatment discontinuation, if needed.	Hold study drug dosing. Participants whose ocular symptoms and signs resolve to ≤ Grade 1 in ≤ 28 days may resume study drug at 1 lower dose level with sponsor approval.

Grade (CTCAE v5.0)	Management	Guidelines for Dose Modification ^a
Grade 4	Complete eye examination. Participants should have weekly symptomatic ocular assessments and repeat eye examinations at least every 6 weeks until resolved to Grade 1 or less, stabilized, or returned to baseline, even after treatment discontinuation, if needed.	Permanently discontinue study drug.

Abbreviations: AE: adverse event; CTCAE: Common Terminology Criteria for Adverse Events.

Note: All participants are recommended to have an EOTV ophthalmic examination, regardless of whether they reported any ocular symptoms or signs. Participants with ongoing Grade 2 or greater ocular symptoms or signs must continue to have ophthalmic examinations at EOTV and during the follow-up period.

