7.7.2. Thrombocytopenia

- Grade 1 or Grade 2 No specific therapy required.
- Grade 3
 - Hold study drug until recovery to \leq Grade 1.
 - Monitor platelet counts weekly until recovery to \leq Grade 1.
 - Discontinue study drug if not recovered to \leq Grade 1 within 42 days.
- Grade 4
 - Hold study drug until recovery to \leq Grade 1.
 - Monitor platelet counts weekly until recovery to \leq Grade 1.
 - Discontinue study drug if not recovered to ≤ Grade 1 within 21 days.
 - Restart study drug with one level dose reduction if recovered to \leq Grade 1.

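### Protocol 5.4 requires study drug to stop after a DLT in the DLT period, Section 7 allows further dosing after five kinds of event that are DLTs, and no text says which governs

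*Protocol*

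**What the plan says.** Section 5.4 of the protocol lets a participant stay on study drug until one of a list of conditions is met. One of these is an "AE requiring study drug discontinuation including, but not limited to, the following events", and under it stands "DLT during dose-escalation window (DLT period". The item has no qualifier for type of event, grade or recovery.

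Section 4.2 counts DLTs that "occur up to Day 21 of Cycle 1 for Schedule A and Day 28 of Cycle 1 for Schedule B". Non-hematologic DLTs are any event at or above "Grade 3 non-hematologic event, including Grade 3 ocular symptoms and signs", less a list of exclusions. Hematologic DLTs include "Grade 4 thrombocytopenia, irrespective of duration" and Grade 4 neutropenia lasting more than 7 days.

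Section 7 sets out what happens to dosing after a toxicity. In Table 7, a participant whose Grade 3 ocular event settles to Grade 1 or less within 28 days "may resume study drug at 1 lower dose level with sponsor approval". (The same words also stand in the Grade 2 row; the Grade 3 row is the one meant here.) Section 7.7.2, on Grade 4 thrombocytopenia, says "Restart study drug with one level dose reduction if recovered to" Grade 1 or less. Sections 7.1.3 and 7.7.1 and Table 8 contain comparable provisions.

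Section 4.5 offers a one-level dose reduction as an alternative to stopping, does not exclude DLTs, and requires the sponsor to approve any reduction beforehand. Section 4.5.1 allows restart at the previous dose when the toxicity is unrelated or is not a DLT. It does not say what follows a DLT.

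**The concern.** This is a first-in-human escalation, and what happens to a participant after a DLT is a safety rule. A participant with Grade 3 keratopathy in Cycle 1 that recovers within 28 days must stop under 5.4 and may continue at a reduced dose under Table 7. Both outcomes can be defended from the text.

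The handling also feeds the data. Section 4.4 makes the percentage of participants with dose reductions or discontinuations for toxicity part of each cohort's safety review, and uses all available data to select the RP2D. SAP 7.1 and 7.2 tabulate relative dose intensity and events leading to discontinuation or interruption. Participants on drug are scanned every 6 weeks (Schedule A) or 8 weeks (Schedule B). Those who stop without progression are scanned every 12 weeks, if feasible. That interval affects ORR, DoR and PFS in the escalation phase.

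**Working it through.** The documents give no figure to reproduce, and no arithmetic is needed. The check sets each event's DLT status under Section 4.2 against the consequence in Section 7, given that 5.4 stops study drug for every DLT in the window.

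| Event in the DLT period | Why it is a DLT | Section 7 | Sponsor approval needed first? |
|---|---|---|---|
| Grade 3 ocular | Named in 4.2.2 | Table 7: resume one level lower if Grade 1 or less within 28 days | Yes (Table 7 and 4.5) |
| Grade 4 thrombocytopenia | 4.2.1, any duration | 7.7.2: restart one level lower on recovery; stop if not recovered in 21 days | Yes (4.5) |
| Grade 4 neutropenia over 7 days | 4.2.1 | 7.7.1: restart one level lower on recovery; stop if not recovered in 21 days | Yes (4.5) |
| Grade 3 diarrhea beyond 72 hours | Outside the 4.2.2 exclusion, which needs resolution within 72 hours | Table 8: hold, then resume one level lower | Yes (4.5) |
| Grade 3 infusion reaction | At least Grade 3, non-hematologic, not on the exclusion list | 7.1.3: may be infused the next day if back to baseline within 12 hours | None stated |

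All five conflict with 5.4.

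Two further cases conflict only by implication:
- **Grade 3 thrombocytopenia with clinically significant bleeding** is a DLT. Section 7.7.2 requires a hold and stops drug only if recovery takes more than 42 days.
- **Grade 2 eye pain or reduced acuity** that does not improve within 14 days of topical therapy may be considered a DLT. Table 7 allows a Grade 2 event that resolves after more than 14 and up to 28 days to resume one level lower.

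The following stop study drug under both sections: transaminases above 8 × ULN, or between 5 and 8 × ULN without improvement in the 7- and 14-day limits; Grade 4 ocular events; Grade 4 diarrhea; Grade 3–4 pneumonitis; Grade 3–4 interstitial cystitis; Grade 4 infusion reactions.

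Next, does Section 7 apply only outside the DLT window?
- No text says so, and none sets an order of precedence. The escalation rules in SAP 3.2.1 do not address it.
- Section 7.2 names the escalation cohorts and schedules their ocular assessments from Cycle 1.
- Re-infusion the day after a Grade 3 reaction to the first dose falls on Day 2, inside the window.
- On Schedule B, Days 8 and 15 of Cycle 1 are dosing days inside the 28-day window, so decisions to re-dose arise there.
- A footnote to Appendix 2 allows the Cycle 2 Day 15 dose to be omitted after significant ocular events in Cycle 1. It gives no grade, so it is only suggestive, but it assumes that such participants go on to Cycle 2.

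**The case against.** The best defense is that the specific rule prevails over the general one. The 5.4 item confines itself to the DLT window of escalation, while Section 7 serves all cycles and both phases, so it need not repeat the exception. Section 5.4 writes an exception for progression and none for DLTs, and 4.5.1 ties restart at the previous dose to toxicity that is unrelated or not a DLT. This reading is plausible, but it is an inference. Section 4.5.1 is silent on a reduced dose after a DLT, and 4.5 offers reduction in place of stopping without excluding DLTs.

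The defense does limit the point. Three stronger readings are tempting, and the documents do not support them:
- **That sites may choose either section.** Four of the five routes resume only at a lower dose level, so 4.5 requires advance sponsor approval. Only the infusion-reaction route lacks that step.
- **That the escalation decision is compromised.** The DLT is counted under the 3 + 3 rule whether or not dosing resumes, and the sponsor medical monitor and investigators review safety before each escalation.
- **That the reach is 13 dose levels** (9 listed on Schedule A plus 4 on Schedule B). That is a count of levels, not of people. At the lowest level of each schedule there is no lower listed level to resume at. Doses up to 7 mg/kg on Schedule A had already been given when this amendment was written.

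**Conclusion.** The contradiction stands. Section 5.4 requires study drug to stop after any DLT in the DLT period. Section 7 allows further dosing after five kinds of event that Section 4.2 makes DLTs, and no text says which governs. Its effect is confined to escalation participants who have one of these DLTs in the window and recover within the stated limits. How many that is cannot be derived from the documents.

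For those participants, exposure, the reduction and discontinuation rates in the Section 4.4 review, and the scan interval all depend on the reading taken. In escalation, ORR and DoR are secondary and PFS is exploratory, so the effect on efficacy falls outside the primary objective. The conclusion rests on reading the 5.4 item as mandatory, which is how its parent item is worded, and on Grade 3 infusion reactions being DLTs because 4.2.2 does not exclude them. It takes no view on which clinical rule is right.

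**What to change.** Reconcile Sections 5.4, 4.5, 4.5.1, 7.1.3, 7.7.1 and 7.7.2 and Tables 7 and 8, so that all state the same consequence of a DLT inside the DLT period. Which rule applies is for the sponsor and investigators to decide. The two cases that conflict by implication can be settled in the same edit.

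The cost is wording in a protocol amendment, with no change to the sample size, the escalation rule or the analyses. An amendment cannot alter exposure that has already occurred. As an optional addition, the DLT listing in SAP 7.2 could show the action taken with study drug after each DLT, so that a reader can see how past cases were handled.
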